8.3.3.3. Expectedness

There are no expected adverse events for this study.

8.3.4 Time Period and frequency of Event Assessment and Follow-up

This retrospective study will only capture past self-reported vaginal infections. There will be no way to tell if it was a potentially related adverse event of the Mosie Kit use in a one time survey. No additional follow-up will be conducted. No identifying information will be collected to allow follow up.

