8.3 Adverse Events and Serious Adverse Events

This retrospective study does not expect there to be any adverse events reported due to participating in the survey. It does however ask questions about any infections that might have occurred during the prior 7 months. While these infections might be completely unrelated to using the Mosie syringe, the response will be evaluated and examined as a percentage of respondents and cycles. It is one of the goals of this study to find out if there might be any adverse events due to the use of the Mosie Kit.

Nonetheless, the definitions and classification for adverse events are outlined below.

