8.3.2 Definition of Serious Adverse Events

According to the FDA a serious adverse event is one that results in death, disability, require and intervention to prevent a disability or permanent damage, birth defect or hospitalization. ER visits without hospitalization are individually evaluated for their severity to determine if they are a serious adverse event.

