8.3.8 Events of Special Interest

Only the events associated with the use of the Mosie Kit will be captured via the survey. If there are any concerns of special interest, the information will be shared immediately with Mosie. This complete study is expected to take approximately 30 days. At the latest, the information will be reviewed for any special items of interest within 2 weeks of the study completion.

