Analysis: Descriptive statistics will be used to analyze perceived safety. Qualitative analysis will be used on any comments made related to safety. Rates of vaginal infections will be analyzed using descriptive statistics.

Secondary Hypothesis 5: The majority of participants indicate they have little to no safety concerns related to using the Mosie Kit. Alternative hypothesis is the majority of participants will be very concerned or extremely concerned about the safety of using the Mosie Kit.

Analysis: Descriptive statistics of self-reported level of concern. Additionally, safety measures such as hand washing, disposing of the syringe after use, and reading the instructions will be examined using descriptive statistics.

Tertiary Hypothesis 1: There will be higher pregnancy rates when using the Mosie Kit when the source of infertility is male-based than when it is female-based. The alternative hypothesis is there will be lower pregnancy rates when using the Mosie Kit when the source of infertility is male-based than when it is female-based.

Analysis: In addition to the descriptive statistics a t-test will be run to examine this hypothesis.

Tertiary Hypothesis 2: There is a difference in pregnancy rates of people with known fertility issues depending on the source of their infertility. Specifically, the following sources of infertility will be examined if sufficient data is available.

- o PCOS
- Endometriosis
- Low AMH or low ovarian reserve
- Low sperm count
- Sperm motility issues
- Unexplained infertility
- Erectile dysfunction
- Performance issues or sexual anxiety, or inability to orgasm with partner.

Page 27

- Vaginismus or vulvodynia
- Tilted uterus
- Multiple uterus/cervix
- Loss of a fallopian tube

The alternative hypothesis is that there will be no difference in the fertility rates associated with different sources of infertility.

Analysis: Descriptive statistics, t-test, correlations and multiple ANOVAs will be used to examine this hypothesis.

Tertiary Hypothesis 3: There will be a difference between individuals who perform 2 insemination instances as described in the instructions and those that follow a different schedule or dosage number. The alternate hypothesis is that there will be no difference between the individuals that perform the minimum 2 insemination instances and those that follow difference dosage schedule.

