9.4 Statistical Analyses

9.4.1 General Approach

Statistical analysis will commence with descriptive statistics for each survey question and plotting of the individual data into scatter plots to understand the data distribution. If any information suggests corrective procedures should be employed, the appropriate transformation or non-parametric test will be used.

Categorical values will be reported using descriptive statistics and frequency of occurrence. Key categorical values will also be converted into a percentage of total responses in order to allow an understanding of the prevalence of the response in the sample. For continuous variables, the means with standard deviations, median and range will be reported.

Qualitative data is only expected as a response to two questions, an open ended safety question and an additional comments question. The responses will be evaluated and categorized. Then the frequency of each category will be provided.

For inferential tests such as t-tests and ANOVAs, a p-value of 0.05 and a confidence interval of 95% will be used for statistical significance. The type of hypothesis will determine whether the specific tests will be one-tailed or two-tailed. Hypothesis seeking to understand whether there is or is not a difference will use a two-tailed test while those seeking a greater than or less than relationship will use a one-tailed test. Correlations among some of the variables will also be examined as appropriate.

Statistical analysis process for each hypothesis has already been described in section 9.1. No baseline analysis is used for cross-sectional studies. No interim analyses are planned for cross-sectional one survey studies.

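### Finding any adverse event of the kit is one of the study's goals, but section 8.3.4 limits capture to vaginal infections, so few or no reports of other harms could reflect the questionnaire as much as safety

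*Combined protocol and SAP*

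**What the plan says.** The protocol describes the scope of safety capture in several places, and they differ.

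- **Goal (8.3).** The section calls it "one of the goals of this study to find out if there might be any adverse events due to the use" of the kit. It says the survey asks about "any infections that might have occurred during the prior 7 months", to be examined as a percentage of respondents and of cycles.
- **Definitions (8.3.1, 8.3.2).** An adverse event is any untoward medical occurrence, though only what the participant provides will be available. The serious-event definition extends to "birth defect or hospitalization", with emergency-room visits evaluated individually.
- **Capture, narrow (8.3.4).** "This retrospective study will only capture past self-reported vaginal infections". The same section says that relatedness to the kit cannot be determined and that there is no follow-up.
- **Capture, wide (8.3.5, 8.3.8).** Section 8.3.5 says adverse events will be captured by the survey. Section 8.3.8 says: "Only the events associated with the use of the Mosie Kit will be captured via the survey".
- **Analysis (9.1, 9.4.1).** Under Secondary Hypothesis 4, "Rates of vaginal infections will be analyzed using descriptive statistics", and safety comments are analysed qualitatively. Section 9.4.1 expects free text from two questions, "an open ended safety question and an additional comments question", with responses categorised and the frequency of each category given.
- **Survey (Appendix A).** The legible closed items on the safety page cover level of concern, treatment of a vaginal infection and type of infection. Several screens are not shown.

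**The concern.** Section 8.3.4 read literally cannot be followed together with 8.3, 8.3.5 and 8.3.8. If it is followed, harms other than vaginal infection reach the database only when a respondent chooses to write about them. The objectives table in section 3 says safety matters because the syringe is inserted into the vagina. Yet no legible closed item asks whether an event such as pain, bleeding, injury or irritation occurred, or whether emergency or hospital care was needed.

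What is at stake is how the safety results can be read. The study could report an infection rate, favourable perception scores under Secondary Hypotheses 4 and 5, and few or no other events. Section 2.3.2 offers the findings to future users as information on safety, and section 10.1.3 allows aggregate results in marketing. A general safety conclusion drawn from that set would go beyond what was asked. Because the survey is anonymous and completed once, the gap cannot be closed after data collection.

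**Working it through.** **1. The plan's own figure.** Section 9.2 gives a 95% margin of 4.4% with 500 surveys and 5% with 384. With half-width = 1.96 × √(0.25/n):

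- n = 500: 1.96 × √(0.25/500) = 4.38%
- n = 384: 1.96 × √(0.25/384) = 5.00%

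Both reproduce. They describe precision for a question that every respondent answers, and say nothing about an event that is reported only if volunteered.

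**2. The sections side by side.**

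| Section | Events captured |
|---|---|
| 8.3 (goal) | Any adverse events due to the kit |
| 8.3 (survey content) | Infections, 7-month look-back, not limited to vaginal |
| 8.3.4 | Past vaginal infections only |
| 8.3.5 | Adverse events in general |
| 8.3.8 | Events associated with kit use |
| 9.1 | Structured rate: vaginal infections; qualitative analysis of safety comments |
| 9.4.1 | Frequencies of categorised free text |

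Only vaginal infection has both a legible closed event item and a planned structured rate.

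**3. What zero reports would show.** This is an illustration; the plan states no upper bound for any harm. If all n respondents are asked about an event, everyone affected reports it, and no one does, the one-sided 95% upper bound is U = 1 − 0.05^(1/n):

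- n = 500: 1 − 0.05^(1/500) = 0.60%
- n = 384: 1 − 0.05^(1/384) = 0.78%

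If only a fraction s of those affected mention it unprompted, zero reports bound the rate of *reported* events at U, and so the true rate at U/s. The chance of no report at all when the true rate is 1% is (1 − 0.01s)^n. The values of s are assumptions; the documents give none.

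| s (assumed) | Bound, n = 500 | Bound, n = 384 | Chance of no report at a true 1%, n = 500 |
|---|---|---|---|
| 1 | 0.60% | 0.78% | 0.7% |
| 0.5 | 1.2% | 1.6% | 8% |
| 0.25 | 2.4% | 3.1% | 29% |
| 0.1 | 6.0% | 7.8% | 61% |

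Since s is unknown, no particular bound can be claimed from the free text. If the volunteered reports are true, their frequency is a lower bound on the frequency among respondents.

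**The case against.** The strongest reply is that 8.3.4 is not the whole plan. The open-ended safety question is a real route for other harms, and its analysis is planned in both 9.1 and 9.4.1. Section 8.3.6 foresees that a participant might reveal a serious event. Section 9.1 adds closed five-point ratings of comfort and of the safety of the process, and Appendix A asks about any concerns raised by the respondent's doctor. The goal in 8.3 can be read as looking for signals rather than estimating rates, and the stated secondary endpoint is perceived safety. All of this stands. It does not remove the conflict between sections. Ratings are opinions rather than event counts, and volunteered comments cannot separate an event that did not happen from one that was not mentioned.

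A reader might infer more than the documents support:

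- *That finding adverse events is the goal of the study.* Section 8.3 makes it one of several; the primary objective is the pregnancy rate.
- *That no frequency could be given for other harms, or that their absence would be wholly a product of the questionnaire.* Section 9.4.1 plans category frequencies, so the absence would be only partly explained that way.
- *That no other harm is asked about.* Some survey screens are not shown, including material next to the safety items, so this cannot be confirmed. If such an item exists, 8.3.4 is wrong and 9.1 omits its analysis, and the text still needs an edit.
- *That the safety evidence is a fixed multiple weaker than it looks.* The ratio in the table is simply 1/s for chosen values of s, and the comparator assumes full reporting when asked, which is optimistic for recall over months.

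**Conclusion.** The point stands, with moderate confidence. The sections disagree on which events are captured. On the legible text, vaginal infection is the only harm solicited by a closed item and given a structured rate. Other harms appear to rest on unprompted comments, so few or no such reports could reflect the questionnaire as much as safety, and should not be presented as evidence that those harms are absent.

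The size depends on an unknown. With 500 respondents, zero reports bound the rate at 0.60% if everyone affected reports, and at 1.2% to 6.0% if the volunteering fraction is between 0.5 and 0.1. That range illustrates the problem and is not an estimate for this survey. The primary pregnancy endpoint is unaffected; what changes is what the study can conclude on safety, which is in its title and its secondary objective.

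**What to change.** Reconcile 8.3, 8.3.4, 8.3.5, 8.3.8 and 9.4.1 so that they state one scope of event capture. Then take one of two routes.

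**Preferred: ask.** Add one required closed item on events during or after kit use, with none and other among the choices, and one on the highest level of care used. Add to 9.1 a table giving each event with its denominator and upper confidence limit. Label these as self-reported events without causal attribution, because 8.3.4 accepts that relatedness cannot be determined and new items would not change that. The care item would cover only the emergency-visit and hospitalization parts of the definition in 8.3.2.

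**Otherwise: narrow the claim.** Restrict safety conclusions to self-reported vaginal infection and perceived safety, report free-text events as volunteered counts only, and narrow the goal in 8.3 to match.

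The cost is two questions in a survey planned at about 10 to 20 minutes, one table and a short protocol edit. Appendix A allows questions to be revised for clarity, but the Statement of Compliance requires IRB approval of any protocol amendment before use. The downside is a slightly longer survey and more minor complaints reported. The second route needs text changes only.

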8.3.5 Adverse Event Reporting

Adverse Events will be captured via the survey but will have occurred in the past. Due to the nature of this study, it will not be possible to follow-up with participants reporting these AEs.

8.3.6 Serious Adverse Event Reporting

It is unlikely that there will be any SAEs related to the Mosie Kit. Even if a participant reveals an SAE, because identifying information will not be collected, it will be impossible to follow up.

8.3.7 Reporting Events to Participants

N/A

8.3.8 Events of Special Interest

Only the events associated with the use of the Mosie Kit will be captured via the survey. If there are any concerns of special interest, the information will be shared immediately with Mosie. This complete study is expected to take approximately 30 days. At the latest, the information will be reviewed for any special items of interest within 2 weeks of the study completion.

8.3.9 Reporting Pregnancy

Pregnancy status will be obtained during the survey. It is not used as an exclusion factor. It is used as an outcome measure.

8.4 Unanticipated Problems

Given the nature of a cross-sectional one-time survey no unanticipated events are expected.

STATISTICAL CONSIDERATIONS

9.1 Statistical Hypotheses and General Statistical Approach

The primary objective is to understand the outcome of using the Mosie kit for Intracervical insemination, i.e. pregnancy rate after its use. Specifically the hypothesis is as follows.

Primary hypothesis 1: Pregnancy rates using the at-home insemination Mosie Kit to deposit semen near or at the cervix (i.e. intracervical insemination) are equivalent or better than traditional in doctor's office intrauterine insemination (IUI). Conversely the null hypothesis is that the pregnancy rates using the at-home insemination Mosie Kit to deposit semen near or at the cervix do not have higher rates of pregnancy than in doctor's office IUI.

Analysis: Comparison of total rates of pregnancy using the Mosie Kit to the 10-20% rate reported for IUI by the American Pregnancy Association.

Primary Hypothesis 2: Pregnancy rates of LGBTQ couples or single women using the Mosie Kit where the female has no know fertility issues will be higher than that of heterosexual couples with a known fertility cause or those that are designated as having an unexplained fertility issue. The alternative hypothesis is that people with no known

fertility issues using the Mosie Kit will have less pregnancies than heterosexual couples with known fertility issues.

Analysis: Rate of pregnancy using the Mosie Kit will be obtained for the following groups: LGBTQ couples where carrying female has no known fertility issues, LGBTQ couples where carrying female has a known fertility issue, Heterosexual people with no known fertility issue, Heterosexual people with a known fertility issue, Single females with no known fertility issue and Single females with a known fertility issue. The rates of each group will be analyzed using descriptive statistics and the aggregate of the 3 groups with fertility issues will be compared with the aggregate of the 3 groups without fertility issues. An ANOVA will be used to compare the differences between groups.

Secondary Hypothesis 1: The participants perceived the Mosie Kit to be easy to use for its intended purpose. The alternative hypothesis is that the participants perceive the Mosie Kit to be difficult to use for its intended purpose.

Analysis: Descriptive statistics surrounding the ease of use on a 5-point likert (very easy to very difficult) will be analyzed on five different aspects of use. Specifically, the steps of using the Mosie Kit (collecting a sperm sample, drawing up the sample in the Mosie syringe, inserting the syringe, and depositing the sperm at or near the cervix) and overall ease of use will be examined. Additionally questions related to use such as comfort, ease and safety of the process, enjoyable and intuitiveness of use (able to use it without instructions) will allow the user to rate their experience from Strongly agree to strongly disagree (5 point scale). The data will be plotted and examined as part of the analysis.

Secondary Hypothesis 2: The participants were able to use the Mosie Kit as instructed using the instructions contained in the kit. The alternative hypothesis is that the participants were not able to use the kit using the instructions contained in the kit.

Analysis: Descriptive analysis of perceived overall success rate will be analyzed. Additionally, descriptive analysis of the frequency of each expected behavior related to use of the kit will be examined.

Secondary Hypothesis 3: The participants reported they used the kit as intended, specifically, using it within 24 hours of initial signs of ovulation and again 24-48 hours after ovulation was confirmed or expected. The alternative hypothesis is that the participants report they did not use the kit as intended with respect to timing (within 24 hours of initial signs of ovulation and again 24-48 hours post ovulation).

Analysis: Frequency rates related to timing of insemination at all reported cycles will be analyzed. The data will be reported in both total number of attempts at each time point as well as percentage of attempts at each time point in comparison with total cycles where the Mosie Kit was used. T-tests will also be used in this analysis. Additionally,

amount of time lying after insemination and position of lying will be analysed using descriptive statistics and correlations with pregnancy rate.

Secondary Hypothesis 4: Participants reported they perceived the Mosie Kit to be a safe way to conceive. The alternative hypothesis is that participants did not perceive the Mosie Kit to be a safe way to conceive.

Analysis: Descriptive statistics will be used to analyze perceived safety. Qualitative analysis will be used on any comments made related to safety. Rates of vaginal infections will be analyzed using descriptive statistics.

Secondary Hypothesis 5: The majority of participants indicate they have little to no safety concerns related to using the Mosie Kit. Alternative hypothesis is the majority of participants will be very concerned or extremely concerned about the safety of using the Mosie Kit.

Analysis: Descriptive statistics of self-reported level of concern. Additionally, safety measures such as hand washing, disposing of the syringe after use, and reading the instructions will be examined using descriptive statistics.

Tertiary Hypothesis 1: There will be higher pregnancy rates when using the Mosie Kit when the source of infertility is male-based than when it is female-based. The alternative hypothesis is there will be lower pregnancy rates when using the Mosie Kit when the source of infertility is male-based than when it is female-based.

Analysis: In addition to the descriptive statistics a t-test will be run to examine this hypothesis.

Tertiary Hypothesis 2: There is a difference in pregnancy rates of people with known fertility issues depending on the source of their infertility. Specifically, the following sources of infertility will be examined if sufficient data is available.

- o PCOS
- Endometriosis
- Low AMH or low ovarian reserve
- Low sperm count
- Sperm motility issues
- Unexplained infertility
- Erectile dysfunction
- Performance issues or sexual anxiety, or inability to orgasm with partner.

Page 27

- Vaginismus or vulvodynia
- Tilted uterus
- Multiple uterus/cervix
- Loss of a fallopian tube

The alternative hypothesis is that there will be no difference in the fertility rates associated with different sources of infertility.

Analysis: Descriptive statistics, t-test, correlations and multiple ANOVAs will be used to examine this hypothesis.

Tertiary Hypothesis 3: There will be a difference between individuals who perform 2 insemination instances as described in the instructions and those that follow a different schedule or dosage number. The alternate hypothesis is that there will be no difference between the individuals that perform the minimum 2 insemination instances and those that follow difference dosage schedule.

Analysis: Descriptive statistics of pregnancy rates for groups with 1, 2, 3 and 4 or more inseminations per cycle will be used. These rates will then be compared to determine if there is a difference.

Tertiary Hypothesis 4: COVID-19 has affected people's family expansion plans. The alternate hypothesis is that COVID-19 has had no effect on people's family expansion plans.

Analysis: Descriptive analysis and a t-test will be conducted to examine this hypothesis.

Tertiary Hypothesis 5: There will be a decrease in pregnancy rates in those using the Mosie Kit during the Months of March - June.

Analysis: Descriptive statistics, graphing, ANOVA and multiple regression analysis will be used to examine this hypothesis.

Additional Analysis will also be conducted to explore why people might choose to use the Mosie Kit, how they actually use it, additional things they do when using the Mosie Kit to complement the experience, and whether they think their health care provider should recommend Mose as an conception option. Most of this analysis will be achieved using descriptive statistics, correlations, and t-tests.

